Recent hospitalization in the past 30 days
Patients on home oxygen, non-invasive ventilator, diaphragmatic pacing, or any
form of nerve stimulator
Patients with pacemaker, defibrillator, left ventricular assist device (LVAD), or
status post cardiac transplantation
Patients with baseline heart rate under 50 bpm or over 100 bpm during last clinic
visit or prior to study at the sleep lab
Patients with unstable cardiopulmonary status judged to be unsafe for sleep study
by the sleep tech and/or the on-call sleep physician in the sleep lab on the night of
the study

- 6. Patients who are unable to complete the required study
- 7. *Patients involved in another investigational study*
- 8. Pregnant women

Number of Research Participants

We will enroll at least 80 subjects in two UH sleep laboratories.

Vulnerable Populations

- 1. Indicate specifically if you will include each of the following special populations by checking the appropriate box:
 - □ Adults unable to consent
 - □ Minors (infants, children, teenagers)
 - \Box Wards of the state
 - □ Foster Children
 - Pregnant Women
 - □ Neonates
 - □ Neonates of Uncertain Viability
 - ⊠ Employees of CWRU or UHHS
 - □ Prisoners
 - ⊠ Illiterate Individuals
 - \boxtimes Non-English Speaking
 - ⊠ University Students
 - □ None
- 2. If excluding pregnant women, illiterate or non-English speaking individuals, provide a scientific rationale for the exclusion. Inconvenience or cost is not an acceptable rationale. *There is unknown risks and benefits of the device to the growing fetus; hence pregnant women are excluded in this study.*
- 3. If the research involves individuals that are included in a vulnerable population, describe the additional safeguards included to protect the rights and welfare of the individuals for each population indicated.

The illiterate individuals are not excluded as long as they make a mark or able to sign their name in the written informed consent form. Also, the written informed consent form will be read to them verbatim before they give their consent.

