Non-sleep providers and sleep providers in UH will order polysomnography as they see patients in their respective clinics. Our schedulers in UH Bolwell Building will call and schedule these patients for the standard, overnight, attended, in-lab sleep study, also known as polysomnography. Subsequently and routinely, the schedulers will e-mail a packet of general information to these patients and add the email recruitment form for the Belun Ring Study. On the email recruitment form itself, there is a phone number and email address for patients to call or e-mail if they are interested or if they decide to opt out. If the research team did not hear anything from the patient after 14 days of emailing the recruitment form, the study coordinators will look up the names of the patients in Enterprise software and make follow-up calls on the patients to ask them if they are interested in participating in the research. Prior making follow-up calls, the study coordinators will do a simple chart review using UH Ambulatory Care EMR to screen patients for eligibility and collect demographics data. If a certain patient is found to be eligible, the study coordinators will call that patient using the phone recruitment script and discuss the Belun Ring Study in detail. The study coordinators will also use this phone interview as a time to answer patient's questions and verify patient's eligibility, in case there are unclear information noted during chart review. If patient is eligible and agreed to participate in the research during the phone interview, the patient's name and related personal information will be placed in the linking sheet and a unique identifier will be assigned to that patient.

- 3. Describe the source (e.g., from what department, EMR, etc.) of the research participants. Enterprise software of the UH Sleep Laboratory is the master schedule where we can see the list of patients scheduled for overnight attended in-laboratory sleep study, also known as polysomnography in the 2 sleep laboratories of University Hospitals namely in Bolwell and Beachwood locations.
- 4. Describe the methods that will be used to **identify** potential research participants. Chart review of the patients listed from the Sleep Lab master schedule will also be done to identify which patient meets eligibility criteria. We will use UH Ambulatory Care for the EMR to do chart review.

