 - \boxtimes Medical record number
 - □ Health plan beneficiary number
 - □ Account number
 - □ Certificate/license number
 - \Box Any vehicle or other device serial
 - □ Device identifiers or serial numbers
 - \Box Web URL
 - □ Internet protocol (IP) address
 - \Box Finger or voice prints
 - □ Photographic images
 - Other: *Sleep study recording data*
- 2. List all other data to be collected for the research study (e.g. laboratory values, physician notes, length of stay, etc.)
 - a. Age, gender, race, weight, height, and BMI
 - b. Past medical and surgical histories
 - c. Concomitant medications
 - d. Physicians' notes on clinic visits for chart review to check subject eligibility

WESTERN	University	Sparta IRB	HRP-503BIO	TEMPLATE: Biom	edical Protocol	
RESERVE	Hospitals	Research Tracking + Administration	Approved:		Prior Version:	08/16/2018

- e. Previous polysomnography (PSG) and home sleep apnea test (HST) in the past
- *f.* All subjective information related to current sleep problem including current CPAP use
- g. SP21256 Sleep Questionnaire
- h. STOP-BANG score
- *i.* UH Pre-sleep Questionnaire part of routine care prior doing the standard polysomnography (PSG)
- *j.* UH Post-Sleep Questionnaire part of routine care after doing the standard polysomnography (PSG)
- *k.* Patient satisfaction survey part of routine care after doing the standard polysomnography (PSG)
- *l.* Arterial blood gas and bicarbonate values if available
- m. Echocardiogram or cardiac MRI results if needed
- n. Total sleep time, Sleep latency, SpO2 nadir, oxygen desaturation index (ODI) and overall apnea-hypopnea index (AHI) in the polysomnography (PSG) during the testing
- o. Total sleep time, SpO2 nadir, and respiratory event index (REI) in the Belun Ring device during the testing

Data Analysis Plan

RStudio Version 1.1.456 will be used to perform an a priori power analysis for the sensitivity of the Belun Ring REI and PSG AHI diagnoses. At alpha = 0.05, power = 0.95, minimum acceptable sensitivity = 0.825, target level of sensitivity = 0.977, a minimum of 35 obstructive sleep apnea (OSA)-positive patients is required. With an estimated 80% of patients receiving a positive polysomnography (PSG) diagnosis of obstructive sleep apnea, recruitment of 42 patients at minimum is necessary. Because not all recruited patients may complete the overnight PSG, we plan to collect data from approximately 50 patients.

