Sensitivity (the proportion of patients correctly diagnosed with OSA) and specificity (the proportion of patients correctly rejected as having OSA) values of sleep scores will be computed, and the area under the receiving operating characteristic (ROC) curve will also be calculated. A sensitivity value of .825 will be considered clinically significant. Pearson correlation will be used to identify the association between OSA and PSG AHI diagnoses. Bland and Altman plots will be generated to demonstrate the degree of identity between the outcomes of the Belun Rung and PSG AHI diagnostic methods.

Additional data such as sleep parameters, stress parameters, and total sleep time will be reported as descriptive analyses (e.g., means and standard deviations).

The primary study endpoint is to investigate the accuracy, sensitivity, and specificity of the Belun Ring in assessing obstructive sleep apnea (OSA) when compared to the gold standard which is polysomnography (PSG). The secondary endpoint is to evaluate the tolerability of the device by the patients.

Confidentiality of Specimens and Banking

Are you storing the specimen(s) for future use for other research projects?

- I am not collecting specimens in this research project
- I am **not** storing specimens in this research project
- □ Yes
- 🛛 No

Confidentiality of Data

- 1. To maintain the confidentiality of the data:
- ☑ I will use a unique study identifier (not derived from the participants' personal identifiers) to code individuals' data and I will store this ID log separate from study data.
- □ Other *(please explain)*:
- 2. How are you storing your electronic data?
 - ⊠ UH Redcap
 - □ CWRU Redcap
 - CWRU's SRE (Secure Research Environment)
 - □ CWRU Box
 - \Box OnCore
 - □ UH Secure Network Drive
 - □ CWRU Secure Network Drive

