- \boxtimes There is **no** direct benefit to research participants.
 - 2. If no direct benefit, state the potential benefit to society or others. *Do not list compensation.*

If the study showed that Belun Ring has high sensitivity and specificity when compared to the gold standard which is the polysomnography (PSG), it can be used as a simple, safe, and inexpensive alternative test to in-lab polysomnography (PSG) testing or as a screening tool prior in-lab polysomnography (PSG) testing. As the device costs less than 10% of a typical home sleep testing device and 1% of an in-lab testing software, its use may revolutionize how obstructive sleep apnea (OSA) is evaluated.

Withdrawal of Research Participants

🛛 N/A

If a participant did not sleep for at least 4 hours during the sleep study, patient will be withdrawn from the research without their consent. Nothing needs to be done in such situation as no follow up is needed.

Alternatives to Participation

 \boxtimes The alternative is for research subjects not to participate.

If patient wishes not to participate, patient will still get the standard overnight in-laboratory polysomnography (PSG) ordered by his or her physician. There will be no change of care regardless.

Costs to Research Participants

 \boxtimes There are no costs to research participants or their insurance companies (there are no clinical visits or billable procedures).

Research Participant Compensation

- \boxtimes There is **no** compensation or reimbursement for research participants.
- \Box There is compensation for research participants.

Describe the schedule, payment method, and payment total of any incentives or compensation that research participants will receive for participation in the research (e.g., gift cards or cash with amount, t-shirts, devices, bags, swag, etc.)

□ There will be reimbursement for research participants. Describe the schedule, payment method, and payment total of any reimbursement that research participants will receive for participation in the research (e.g., gift cards or cash with amount, etc.)

Compensation for Research Related Injury

Describe who will pay for the costs of medical treatment and/or compensation in the event of a research related injury:

- $\Box\,$ Funding agency is providing some/all payment for injury
- \boxtimes Funding agency is providing no payment for injury
- \square N/A

Provisions to Monitor the Data to Ensure the Safety of Research Participants

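### Exclusion 6 has no time point or scope and there is no rule for failed ring recordings, so the plan permits ring removals and failures to be dropped after the night from both the accuracy and the tolerability results

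*Combined protocol and SAP*

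**What the plan says.** - **Exclusion Criteria, item 6:** "Patients who are unable to complete the required study". No time point, assessor or definition of the study is attached. Item 5, by contrast, is a safety judgement made "by the sleep tech and/or the on-call sleep physician in the sleep lab on the night of" the study.
- **Recruitment Methods:** eligibility is checked before the night. The coordinators "do a simple chart review using UH Ambulatory Care EMR to screen patients for eligibility and collect demographics data", and then confirm eligibility by telephone.
- **Withdrawal of Research Participants:** "If a participant did not sleep for at least 4 hours during the sleep study, patient will be withdrawn from the research". This is known only after the recording. The same section has its N/A box ticked.
- **Data Analysis Plan, sample size:** "Because not all recruited patients may complete the overnight PSG", the minimum of 42 is raised to about 50. This is the only allowance for non-completion, and it concerns the PSG.
- **Data Analysis Plan, endpoints:** the primary endpoint is accuracy, sensitivity and specificity against PSG. "The secondary endpoint is to evaluate the tolerability of the device by the patients". No measure or denominator for tolerability is given, and no analysis set is defined for either endpoint.
- **List of Data to be Collected:** from the ring, only total sleep time, SpO2 nadir and the respiratory event index. A routine post-sleep questionnaire and a satisfaction survey are listed but not linked to tolerability.
- **Risks to Research Participants:** pressure discomfort is foreseen and leads to refitting with another size. Nothing is said about recording removal of the ring.

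**The concern.** Whether a patient completes the night is an outcome of the study, yet it appears among the eligibility criteria. If item 6 is applied after the recording, a participant who took the ring off, or whose ring recording failed, can be classed as ineligible and leave every denominator. For this study those are informative participants: ring removal is a tolerability event, and a night with a valid PSG but no usable ring result is a non-diagnostic test.

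The stated purpose is to judge the ring as an outpatient evaluation, possibly as an alternative to PSG or a screening step before it. In that use, a test that returns no result has not found the disease. Accuracy computed only where the ring worked would overstate what a referring clinician can expect, and tolerability computed only among those who kept the ring on would say little.

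**Working it through.** **1. The plan's own figure.** Inputs from the Data Analysis Plan: "At alpha = 0.05, power = 0.95", "minimum acceptable sensitivity = 0.825, target level of sensitivity = 0.977", and a stated minimum of 35 OSA-positive patients.

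Arcsine formula, one-sided: n = [(1.645 + 1.645) / h]², with h = 2·asin(√0.977) − 2·asin(√0.825) = 0.559. This gives 34.7, so 35. The exact one-sided binomial test at n = 35 rejects with 33 or more detected (alpha 0.042, power 0.954). The stated 35 therefore reproduces as a one-sided calculation, and it does not depend on item 6.

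**2. Is power at risk?** The allowance from 42 to 50 is (50 − 42)/50 = 16% loss. The plan expects 80% of patients to be PSG-positive.

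- With the enrolment of at least 80 given under Number of Research Participants and Study Design: 80 × 0.84 × 0.80 = 53.8 PSG-positive patients, well above 35.
- With about 50: 50 × 0.84 × 0.80 = 33.6. At n = 34 the exact one-sided test (32 or more detected, alpha 0.048) still has power 0.957.

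Power is not the issue. What remains is bias.

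**3. What dropping ring failures could hide in the primary endpoint.** Let S be sensitivity among PSG-positive patients with a usable ring result, and f the share of PSG-positive patients (with a valid PSG) who have none. Counting the latter as not detected, sensitivity = S × (1 − f). It falls below .825 when f > 1 − 0.825/S.

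The documents do not give f, so a range is assumed. S = 0.977 is the plan's target; S = 0.90 is an assumption.

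| f | S = 0.90 | S = 0.977 |
|---|---|---|
| 5% | 0.855 | 0.928 |
| 10% | 0.810 | 0.879 |
| 15% | 0.765 | 0.830 |
| 20% | 0.720 | 0.782 |

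Crossing points: 1 − 0.825/0.90 = 8.3%; 1 − 0.825/0.977 = 15.6%. With 80 enrolled, 80 × 0.80 = 64 are expected to be PSG-positive. The criterion is then missed from 6 losses at S = 0.90 (0.90 × 58/64 = 0.816) and from 10 losses at S = 0.977 (0.977 × 54/64 = 0.824).

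**4. An indirect reference point.** The Background describes a 2014 finger-photoplethysmography study in which 65 of 73 referred patients were monitored and had valid results. The other 8 (8/73 = 11.0%, exact 95% CI 4.9% to 20.5%) are not explained and need not be device failures. A loss of that size would turn 0.90 into 0.80 and 0.977 into 0.87.

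**5. Tolerability.** For illustration only: if 5 of 50 fitted participants removed the ring, the all-fitted rate is 10% (exact 95% CI 3.3% to 21.8%). If those 5 were excluded, the rate would be 0 of 45. The plan does not say which denominator applies.

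**The case against.** The strongest reply is that item 6 need not work after the fact. It stands in an eligibility list, eligibility is screened before the night, and the item can be read as a judgement of capability at screening or on arrival. The study it refers to may well be the PSG, which is how the neighbouring criteria use the word and the only non-completion that the sample-size paragraph mentions. On that reading, a patient with a valid PSG and a failed ring is not touched by item 6, and a patient without a PSG has no reference diagnosis and cannot enter sensitivity or specificity under any rule. All of this stands: both readings are open.

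A reader might go further and infer that completion can only be known after the night, that ring failures will be removed, or that tolerability is close to 100% by construction. The documents do not support these. No section orders ring-intolerant participants out of the results. Discomfort leads to refitting, not exclusion, and the questionnaire and survey could capture tolerability although they are not assigned to it. The plan is silent rather than fixed at a favourable answer.

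Nor do the numbers show that the .825 criterion will be missed. At the plan's target of 0.977, losses up to 15% stay above it. At the 80% sensitivity reported for the earlier Colorado study (AHI cutoff 15), it is missed with no failures at all.

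What remains is that nothing in the plan settles the reading. The 4-hour rule shows that removal after the night is already part of the design, and deleting item 6 alone would not close the gap.

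**Conclusion.** The point holds as a permission, not as an instruction. An exclusion without time point or scope, a withdrawal rule applied after the night, and the absence of an analysis set and failed-recording rule together allow participants without a usable ring result to be dropped from both endpoints. The effect, if it occurs, is upward bias in accuracy and tolerability; power is not materially affected.

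Its size cannot be stated, because no ring failure rate is given. The crossing points of 8.3% and 15.6% rest on sensitivities of 0.90 (assumed) and 0.977 (the plan's target) among evaluable patients, and on the deliberately unfavourable convention that every missing ring result is a missed case. They show that plausible losses could change the conclusion, not that they will. This is a cheap improvement, best made before any data are seen.

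**What to change.** - Limit exclusion 6 to inability known before the ring is applied, and state which study it refers to.
- Keep every participant fitted with the ring in the tolerability denominator. Record ring removal, its reason, and failed or partial recordings.
- Among participants with a valid PSG, report the ring failure rate with an exact 95% CI.
- Report participants withdrawn under the 4-hour rule separately, with their number.
- Add a sensitivity analysis of the primary endpoint in which patients with a valid, positive PSG but no evaluable ring result count as not detected. Patients without a valid PSG stay out of sensitivity and specificity.

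The cost is wording in the eligibility and analysis sections plus a small added data field, since the current list has none for ring removal. The downside is that reported performance may be slightly lower.

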5. Describe the feasibility of recruiting the required number of suitable research participants within the agreed recruitment period. For example, how many potential research participants do you have access to?

There are total of 10 beds if we combine the two UH sleep laboratories. Both sleep laboratories operate 7 nights per week except on major federal holidays. One-third of the beds are for pediatric patients and two-thirds are for adult patients. Out of 10 beds, there will be 6 beds reserved for adult patients every night. Considering the possibility of no-show or some patients meeting the exclusion criteria, we are looking into potentially 2-3 research participants per night.

Setting

The sites and locations where the research team will conduct the research is the same as the physical location where research procedures will be performed and they are as follows:

- 1. Department of Pulmonary, Critical Care, and Sleep Medicine at [name]
- 2. Residence Inn Marriott at [name]

However, the main location where the research team will identify and recruit potential research participants will be in Department of Pulmonary, Critical Care, and Sleep Medicine at [name]

Consent Process

Indicate whether you will be obtaining consent:

 ∑ Yes
 □ No

Sparta IRB

University Hospitals

If yes, answer the following questions:

- 1. Describe where the consent process will take place:
 - a. Department of Pulmonary, Critical Care, and Sleep Medicine at [name]
 - b. Residence Inn Marriott at [name]
- 2. The time that will be devoted to the consent discussion: *15-30 minutes*
- 3. Any waiting period available between informing the prospective subject and obtaining the consent:

From the time we e-mailed the recruitment form, we will wait 14 days before doing simple chart review and making follow-up calls to prospective subjects. If patients verbalized interest during the phone call interview, they will not sign the written informed consent until the night of their scheduled polysomnography; hence, waiting period from informing prospective subject to obtaining written consent is variable but will most likely be more than 14 days.

4. Steps that will be taken to ensure the research participants' understanding:

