This prospective, single-blind, non-randomized, single-visit study will recruit at least 80 patients who are suspected to have obstructive sleep apnea (OSA) and are scheduled to undergo polysomnography (PSG) in a sleep laboratory for evaluation of obstructive sleep apnea. Patient recruitment starts with e-mailing recruitment forms to the patients who have been scheduled for polysomnography. On the email recruitment form itself, there is a phone number and e-mail address for patients to call or e-mail if they are interested or if they decide to opt out. If the research team did not hear anything from the patients after 14 days of emailing the recruitment forms, the study coordinators will look up the names of the patients in Enterprise software which is the master schedule for all patients going for overnight in-lab polysomnography. Subsequently, the study coordinators will do a simple chart review using UH Ambulatory Care EMR to screen patients for eligibility and collect demographics data. If a certain patient is found eligible, one of our research team will make follow-up call to that patient and determine if patient is interested in participating in the research. During this phone interview, the phone recruitment script will be used to verify the subject's eligibility criteria, discuss the Belun Ring study further, and answer all the patient's questions. If patient is eligible and agreed to participate in the research during the phone interview, the patient's name and related personal information will be placed in the linking sheet and a unique identifier will be assigned to that patient. Then, the list of patient's unique identifier will be e-mailed to the sleep technician prior to the scheduled sleep study. All communication with the sleep technician will be done through UH e-mail addresses within UH premises. On the other hand, if the patient got the e-mail and called the research team to opt out in the trial, that patient will be not be called and no chart review will be done in the EMR for that patient.

On the night of the scheduled polysomnography (PSG), Sleep Questionnaire and 2 copies of the written informed consent will be presented to the patient together with other routine care pre-sleep questionnaires. The Sleep Questionnaire will be completed by the patient prior the start of the polysomnography. Our CREC certified sleep technicians will discuss the consent form in detail

	Sparta IRB	HRP-503BIO	TEMPLATE: Biom	edical Protocol	

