No blood tests are needed prior the overnight polysomnography (PSG) study but patients will be given several questionnaires to complete before and after testing with polysomnography (PSG) Overnight standard laboratory-based polysomnography (PSG) will be performed using Sleepworks software on all sites. Sleep will be documented using the electroencephalography (EEG), bilateral electrooculography (EOG), and submental electromyography (EMG). Other routine measurements when performing standard polysomnography (PSG) include the electrocardiogram (ECG), nasal pressure transducer airflow, oronasal airflow (thermistor or thermocouple), thoracic and abdominal respiratory inductance plethysmography (RIP), traditional finger pulse oximeter, body position, bilateral leg electromyography (EMG), video recording, and a surface microphone attached above the sternal notch for detection of snoring. The technician will be attaching all these electrodes and channels to the patient according to the American Academy of Sleep Medicine (AASM) guidelines. Meanwhile, the Belun Ring will be worn on the proximal phalanx of index finger of the opposite hand so that it will not interfere with the measurement of the traditional finger pulse oximeter. After completing the polysomnography (PSG), no need for follow-up visit nor blood tests.

Study Timeline

Once we have the target number of patients, we will stop recruitment.

WESTERN	University	Sparta IRB	HRP-503BIO	TEMPLATE: Biom	edical Protocol	
RESERVE	Hospitals	Research Tracking + Administration	Approved:		Prior Version:	08/16/2018

	Pre-Screening	Visit 1	Visit 2	Wrap Up
Estimated time requirement	15 minutes	15-30 minutes	6-8 hours	1-2 weeks
Data Collection	Х			
Phone Call Questionnaire		Х		
Study Procedure			Х	
Data Analysis				Х

Radiation and Radioactive Substances

- 1. Does the research involve the use of radiation or radioactive substances?
 - \Box Yes \boxtimes No

ClinicalTrials.gov Information

This study is currently registered on ClinicalTrials.gov with the following Identifier: NCT03997916.

List of Data to be Collected

Note: If using REDCap, all selected identifiers below must be indicated as PHI.

- 1. Indicate what identifiers you will collect
 - 🛛 Name
 - Address (e.g., Zip code, other geographical designation, etc.)
 - Dates related to an individual (e.g., Date of admission, birth, surgery, etc.)
 - \boxtimes Telephone number
 - □ Fax number
 - \boxtimes Email address
 - □ Social security number

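### The stated minimum of 42 recruits should be 44 (35/0.80), and the Data Analysis Plan's figure of about 50 patients is not reconciled with the commitment to at least 80 elsewhere in the protocol

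*Combined protocol and SAP*

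**What the plan says.** The sample-size paragraph of the Data Analysis Plan takes alpha 0.05, power 0.95, a minimum acceptable sensitivity of 0.825 and a target sensitivity of 0.977. From these it concludes that "a minimum of 35 obstructive sleep apnea (OSA)-positive patients is required". It converts positives to recruits as follows: "With an estimated 80% of patients receiving a positive polysomnography (PSG) diagnosis of obstructive sleep apnea, recruitment of 42 patients at minimum is necessary". Then, because some recruits may not finish PSG, it adds: "we plan to collect data from approximately 50 patients".

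Two other sections give a different total. Number of Research Participants states: "We will enroll at least 80 subjects in two UH sleep laboratories". Study Design says that the study "will recruit at least 80 patients".

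Two further sections bear on the count. Study Timeline says: "Once we have the target number of patients, we will stop recruitment", and gives no number. Withdrawal of Research Participants adds a loss that the sample-size paragraph does not mention: "If a participant did not sleep for at least 4 hours during the sleep study, patient will be withdrawn from the research".

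**The concern.** There are two faults. The step from 35 positives to 42 recruits does not follow from the stated 80% positivity; it looks as if 20% was added where the plan should have divided by 0.80. In addition, the only recruitment figure with a statistical derivation (42, raised to about 50) is not the figure to which the protocol body commits (at least 80).

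The second fault could affect conduct, because the rule for ending recruitment refers to a target without naming it. Someone working from the Data Analysis Plan alone could take that target to be about 50. The stated 0.95 power would then have almost no margin, although the 50 is presented as already allowing for incomplete studies.

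**Working it through.** **Inputs, all from the Data Analysis Plan unless noted.** Alpha 0.05 (sidedness not stated); power 0.95; sensitivity 0.825 under the null and 0.977 under the target; 35 positives required; 80% expected positive; minimum 42 recruits; about 50 planned. At least 80 comes from Number of Research Participants and Study Design.

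**Step 1: the 35 positives.** One-sided arcsine formula: n = ((z_0.95 + z_0.95)/h)^2, with h = 2 asin(sqrt(0.977)) - 2 asin(sqrt(0.825)) = 0.559. This gives 34.67, so 35. As a check, an exact one-sided binomial test with 35 positives, passing at 33 or more detected, has alpha 0.0419 and power 0.954. The 35 therefore reproduces with a one-sided alpha of 0.05.

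**Step 2: from positives to recruits.**
- Correct conversion: 35/0.80 = 43.75, so 44. Check: 44 x 0.80 = 35.2.
- The plan's 42: 35 x 1.20 = 42.0 exactly. Check: 42 x 0.80 = 33.6, below 35.
- For 42 to suffice, positivity would have to be 35/42 = 83.3%.
- Chance of at least 35 positives if the count is Binomial(N, 0.80): 0.378 at N = 42, 0.617 at N = 44, 0.969 at N = 50.

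**Step 3: 50 against 80.**
- Allowance implied by 50: 1 - 42/50 = 16% from 42, or 1 - 44/50 = 12% from 44.
- Loss needed to go from 80 enrolled to 50 with data: 1 - 50/80 = 37.5%. No section gives this or any other loss rate.
- Expected positives: 50 x 0.80 = 40; 80 x 0.80 = 64. Both exceed 35.

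**Step 4: what each total buys.** Exact binomial test of 0.825, true sensitivity 0.977, power averaged over Binomial(N, 0.80) positives, where N is the number of evaluable patients:

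| N evaluable | one-sided 0.05 | one-sided 0.025 |
|---|---|---|
| 44 | 0.920 | 0.816 |
| 45 | 0.928 | 0.826 |
| 49 | 0.948 | 0.879 |
| 50 | 0.952 | 0.891 |
| 80 | 0.998 | 0.992 |

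The one-sided 0.05 column is the basis that reproduces 35; the other corresponds to two-sided 0.05. At 44 the averaged power is below 0.95 even though expected positives exceed 35, because the number of positives varies around its mean.

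**The case against.** The strongest reply is that this has almost no practical effect. Two sections commit to at least 80, which is the natural reading of the unnamed target, and at 80 a two-patient slip in a minimum is irrelevant. That stands, and it is why the point is minor. It does not make the paragraph correct: 42 still does not follow from 35 and 80%.

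One might try to rescue 42 through another formula. The normal approximation with null and alternative variances gives 32.88, so 33 positives, and 33/0.80 = 41.25 also rounds up to 42. But the plan states 35, so this route does not explain its text.

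It can also be said that 50 and 80 are different quantities: patients with data and patients enrolled. That is fair, and it means that writing 80 where 50 stands would not repair the sentence. Yet a reader who infers 80 enrolled and 50 analysed goes beyond the documents. The 50 is introduced as the figure that already allows for incomplete PSG, and a 37.5% loss appears nowhere.

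The shortfall at about 50 should not be overplayed either. Losing one patient moves power only from 0.952 to 0.948; larger losses matter more (0.928 at 45), but no rate is given.

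Finally, a reader might count no-shows as further erosion of the enrolled number, citing the feasibility text in Recruitment Methods ("Considering the possibility of no-show or some patients meeting the exclusion criteria"). That sentence concerns how many participants to expect per night. Written consent is signed only on the night of the PSG, so a no-show has not yet been enrolled. The losses after consent that the documents name are incomplete PSG and sleep under 4 hours.

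**Conclusion.** The point holds, as a minor one. On the plan's own inputs the minimum is 44, not 42, an understatement of two patients. The figure of about 50 is unreconciled with at least 80, while the end of recruitment depends on a target that is not named.

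Three stronger conclusions are not supported:
- **The study is underpowered for sensitivity.** With 80 evaluable, averaged exact power is 0.998 at one-sided 0.05 and 0.992 at one-sided 0.025.
- **Recruitment will stop at 50.** No section says so.
- **44 recruits secure 0.95 power.** They only bring expected positives to 35; on the averaged exact basis, 44 evaluable give 0.920 and 50 give 0.952, at one-sided 0.05.

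The 44 rests on the plan's 35 and 80% alone. The power figures also assume an exact test, a true sensitivity of 0.977 and positives distributed Binomial(N, 0.80). The plan does not state sidedness, so both are shown; the conclusion at 80 is the same under either.

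**What to change.** 1. In the Data Analysis Plan, change 42 to 44 and show 35/0.80 = 43.75. Describe 44 as the number at which expected positives reach 35, not as a guarantee of 0.95 power.
2. Make the at least 80 enrolled, already stated in Number of Research Participants and Study Design, the single recruitment target, and name it in Study Timeline.
3. In the Data Analysis Plan, replace the unexplained figure of about 50 with the number of evaluable patients that the 80 enrolled are expected to yield after incomplete PSG and sleep under 4 hours. The investigators must supply this expectation, since the documents give no rate.

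The cost is protocol and analysis-plan wording only. No patients are needed beyond the 80 already committed.
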